#### i.iv. Stratification of Kessler 6-item (K6) scale scores

The Kessler 10-item scale (K10) has been widely used in the Australia National Studies to assess the low, moderate, high and very high levels of psychological distress (Enticott et al., 2022). The K6 scale is comprised of six items selected from K10 which shows equivalent usefulness in terms of internal validity, measurement timeframe, and the assessment for psychological distress (Furukawa, Kessler, Slade, & Andrews, 2003). Four strata of scores (Low 6-9; Moderate 10-14; High 15-18; Very high 19-30) were used to define the four levels of psychological distress, which were generated and validated

from the normative data from the 2007 Australian National Survey of Mental Health and Wellbeing (Slade, Grove, & Burgess, 2011).

#### i.v. CONSORT flow diagram

The template for the Consolidated Standards of Reporting of Trials (CONSORT) flow diagram was erroneously omitted in v1 and has been added as Figure 5.1.

## 1. Study design

The *PharMIbridge* Randomised Controlled Trial (RCT) will evaluate the effectiveness of an individualised, pharmacist-led support service for people with severe and persistent mental illness (SPMI) focusing on adherence and the management of physical co-morbidities, compared to standard care involving a Medication Review Service (MedsCheck). Community pharmacies will be randomised using a 1:1 ratio, to either the Intervention Group (IG) or Comparator Group (CG) within four Australian regions (Australian Capital Territory (ACT), Hunter New England (HNE), Northern Sydney (NS), Regional Victoria (VIC)). All recruited pharmacy staff will receive Blended-Mental Health First Aid (BMHFA) training. Additionally, IG pharmacists will receive training on adherence, goal setting, motivational interviewing, managing physical health concerns and complex issues relating to psychotropic medication. Details on the study design of the *PharMIbridge* RCT are published elsewhere (Wheeler et al., 2020).

#### 1.1 Purpose and scope

The purpose of this document is to minimise bias by defining and making publicly available our analysis approach prior to reviewing or analysing any trial data. The following statistical analysis plan (SAP) has been developed to inform the analysing and reporting of the main outcomes from the *PharMIbridge* RCT including our approach to expected protocol deviations, withdrawals, missing data, and loss to follow up. Outcomes considered in this SAP are the primary and key secondary outcomes that will inform both the main effectiveness findings of the trial and future Medical Services Advisory Committee (MSAC) applications. In this SAP, broad statistical analysis principles are outlined, primary and secondary trial outcomes are described, along with appropriate methods for statistical comparison. Other outcomes, such as those related to the *PharMIbridge* training program outcome and qualitative data analysis will be reported elsewhere. This SAP should not be taken as a comprehensive plan for all future analyses using RCT data.

## 2. Analysis principles

**General analysis:** Comparative analyses will allow for the clustered nature of the data and baseline values will be adjusted in the models. The cluster will be the community pharmacy and the analysing unit will be the individual consumer participant.

**Stratified analysis:** Stratified analyses will be conducted based on the metropolitan or non-metropolitan location of community pharmacies.

**Intention-to-treat analysis:** All analyses will be undertaken based on the 'intention-to-treat' principle, that is, participants' data will be analysed according to the group to which they were initially allocated (White et al., 2011).

**Per-protocol analysis:** Due to the impact of the novel coronavirus (COVID-19) pandemic, consumer participants may have not completed each data collection milestone within the targeted timeframe. For example, a 6-month review including a follow-up survey should be completed 6 months after the initial intervention/comparator service interview with the participating pharmacist. However, some consumer participants were unable to attend appointments as scheduled due to state-wide lockdowns and other factors associated with the pandemic such as social distancing. A per-protocol sample is defined if consumer participants who have completed the initial pharmacist intervention/comparator service interview within 8 weeks after completing the baseline survey, and if they have completed the 6-month follow-up survey within 16-32 weeks after the initial pharmacist intervention/comparator service interview. Participants, who have received extra medication management services, such as a home medicines review (HMR), will be excluded from the perprotocol analysis to eliminate potential contaminations between groups. Per-protocol analyses will be undertaken for the co-primary outcomes (subjective and objective measures of adherence) and several key secondary outcomes.

**Exclusions**: Data will be excluded if participants actively withdraw and request that their data are destroyed.

**Presentation of results**: Descriptive data will be summarised as mean (SD) or median (range or 25-75th percentile) for continuous variables and frequency (percentage) for categorical variables, respectively. Between-group comparisons will be calculated and presented with 95% confidence intervals wherever possible.

**Level of significance**: The statistical significance level will be set at less than 5%.

**Statistical software**: All analyses will be performed using Stata 17 (StataCorp) or SPSS Version 27 (IBMCorp).

#### 3. Trial profile

The progress of clusters and individuals through phases of the trial will be presented in a flow diagram in accordance with the CONSORT extension statement for cluster trials (Campbell, Piaggio, Elbourne, & Altman, 2012). An outline of the flow diagram is presented in Figure 4.1.

#### 3.1 Data sources and analysis samples

The data will be collected from a number of sources depending on the type of information collected and the availability of the data. There are six samples used in this analysis plan, which are defined below:

**Baseline completion data sample**: Consumer participants who consented to participate in the study and completed a baseline process, which included a baseline survey and an initial interview with the pharmacist, will be considered members of the baseline completion data sample.

**Survey completion data sample:** Consenting participants will be assessed at baseline and reassessed at the 6-month endpoint using online questionnaires. Consumer participants will be considered members of the survey completion data sample if they completed surveys at both the baseline and 6-month points.

**Service completion data sample:** Consumer participants allocated in different arms will receive relevant intervention and comparator services. Clinical implementation outcomes relating to these services will be recorded by participating pharmacists using a purpose-designed research module developed by Guild Link. Consumer participants will be considered members of the service completion data sample if they have completed at least the initial pharmacist interview for an intervention or comparator service.

Linked hospital data sample: All consented consumer participants' hospital admission and emergency department visit data in the relevant jurisdiction will be linked based on a participant's identifiers, including name, date of birth, sex, and current residence. Consumer participants who have completed the baseline process, and whose hospital data were provided by the relevant data linkage agencies will be considered members of the linked hospital data sample.

Linked MBS/PBS data sample: All consumer participants with a valid consent form for MBS and PBS data linkage will be linked for health care (MBS) and pharmaceutical utilisation (PBS) data through Service Australia. Consumer participants successfully linked to the MBS and PBS database will be considered members of the linked MBS/PBS data sample.

**Pharmacy dispensing history data sample:** Consumer participants with dispensing history records provided by Guild Care or participating pharmacies will be considered members of the pharmacy dispensing history data sample.

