**Primary analysis:** A mixed-effects logistic regression model will be applied to compare the medication's adherence rate over the 6 months after initial intervention/comparator service between IG and CG. RCT group will be entered as fixed effect and pharmacy entered as a random intercept to account for possible non-independence of observations from participants who attend the same pharmacy. The baseline value of the outcome variable will be included as a covariable in the model. The effect estimate will be reported as an odds ratio with 95% confidence interval.

**Sensitivity analysis:** To assess the robustness of the results, sensitivity analysis will be performed for this primary outcome, using the linked PBS data sample.

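### The linked hospital sample keeps only participants who had the initial pharmacist interview, which conflicts with the intention-to-treat statement, and the other service-anchored outcomes give unserved participants no start date

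*SAP*

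**What the plan says.** Section 2 of the SAP applies intention-to-treat to all analyses and explains it to mean that "participants' data will be analysed according to the group to which they were initially allocated". The only exclusion given there is this: "Data will be excluded if participants actively withdraw and request that their data are destroyed".

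Section 3.1 describes the baseline completion sample as people who consented and "completed a baseline process, which included a baseline survey and an initial interview with the pharmacist". It says that hospital admission and ED data will be linked for all consented participants, but then restricts the linked hospital data sample to "Consumer participants who have completed the baseline process, and whose hospital data were provided by the relevant data linkage agencies". The service completion sample is defined by the same contact: people belong to it "if they have completed at least the initial pharmacist interview for an intervention or comparator service". The linked MBS/PBS sample needs only valid consent and successful linkage. The dispensing sample needs only dispensing records.

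The outcome windows start at that contact. Section 4.1.1 compares adherence "over the 6 months after initial intervention/comparator service", and Tables 4.1 and 4.2 use the six months after the initial service for GP visits and for the four hospital and ED outcomes. For adherence, section 4.1.1 also takes the six months before the service as the pre-intervention period, and the baseline value is a covariate in the model.

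Section 2 expects lockdowns to have disrupted appointments. It limits the survey-to-interview interval to 8 weeks, but only for the per-protocol sample.

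**The concern.** The initial interview is delivered as either the intervention or the comparator service, so whether and when it happens follows the pharmacy's allocation. A main-analysis sample that requires it is a sample of people who started the service. In a population with severe and persistent mental illness, those who consent but never attend may well be the less stable ones, and hospital and ED use are outcomes on which they could differ.

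The two services differ in content, so uptake and waiting time could differ by arm. If they do, and if non-attendance goes with more hospital use, the comparison among those served is distorted even when the service has no effect.

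A related gap affects objective adherence (one of the co-primary outcomes) and GP visits. Unserved people can belong to those samples, but a window that opens at a service they never had cannot be drawn for them. Section 1.1 says the SAP covers expected deviations, missing data and loss to follow-up, so this rule belongs in this document.

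**Working it through.** **1. Sample definitions side by side (section 3.1 against section 2).**

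| Outcome group | Sample requires the interview? | Window starts at the service? | Participant never served |
|---|---|---|---|
| Four hospital/ED outcomes | Yes, through the baseline process | Yes | Excluded by definition |
| Objective adherence (co-primary) | No | Yes | Can be a member, but has no start date |
| GP visits | No | Yes | Can be a member, but has no start date |

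The first row is a direct conflict. Linkage is planned for all consented participants, so the unserved are removed by the sample rule and not for want of linkage. Section 2 does not list that exclusion. The other two rows are an omission: no rule says how to derive the outcome.

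**2. Waiting time.** Only the adherence outcome has a stated six-month pre-service period. For it, time between survey and service counts as baseline. Taking six months as 26 weeks, the share of the baseline period filled by a wait of w weeks is w/26:

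- 4 weeks: 4/26 = 15.4%
- 8 weeks: 8/26 = 30.8%
- 12 weeks: 12/26 = 46.2%

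The main analysis sets no upper limit on w.

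**3. Illustration for the hospital sample.** The SAP states no figure to reproduce here. Let p be the rate of any hospital or ED record among all allocated participants, f the share never served, and q the rate among the never served. With no true effect, the rate among those served is (p − f·q)/(1 − f).

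Inputs: p = 0.25 in both arms, taken loosely from SAP section i.ii, where almost three quarters had no admission and/or ED record. The values of f and q are assumptions. Arm A has f = 0.05 throughout.

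| q | f in arm B | Arm A, served | Arm B, served | B − A (points) | Odds ratio |
|---|---|---|---|---|---|
| 0.40 | 0.10 | 0.230/0.95 = 24.2% | 0.210/0.90 = 23.3% | −0.9 | 0.953 |
| 0.40 | 0.15 | 24.2% | 0.190/0.85 = 22.4% | −1.9 | 0.901 |
| 0.50 | 0.10 | 0.225/0.95 = 23.7% | 0.200/0.90 = 22.2% | −1.5 | 0.921 |
| 0.50 | 0.15 | 23.7% | 0.175/0.85 = 20.6% | −3.1 | 0.835 |

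If q = p, or if f is the same in both arms with the same q, the difference is zero. Swapping the arms reverses the sign.

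**The case against.** The strongest reply is that section 2 describes intention-to-treat only as analysis by allocated group, and everyone analysed does stay in that group. Both arms have an initial interview, so the rule is formally the same in each. Nothing in the SAP shows that non-start differs by arm or is related to outcome. This stands as a limit on the size of the problem. It does not remove the conflict: the statement covers all analyses and lists one exclusion, and the hospital sample adds another that depends on receiving the service.

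Some safeguards exist. Section 3 promises a CONSORT diagram for clusters and individuals, which should show much of the non-start. The per-protocol analysis gives a check on long waits, but it also requires the interview and so cannot restore the unserved. Section i.iii imputes about 13% missing follow-up adherence and uses service completion status as a predictor. That may mean unserved people are in the adherence dataset, or the variable may mean completing the full service; the text does not say. Hospital, ED and GP outcomes are not imputed.

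A reader might infer three stronger things that the SAP does not support:

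- **Every linked outcome is conditional on service receipt.** Only the hospital sample has that condition. For adherence and GP visits the fault is a missing start date.
- **Late-served people are lost, or their waiting time becomes baseline for every outcome.** Late-served people stay in. The pre-service baseline period is stated only for adherence. Tables 5.5 and 5.6 have a baseline column for GP and hospital outcomes, but its period is not defined.
- **The bias is known to favour one arm.** The non-start shares above are assumed, and the direction follows from which arm is given the larger one.

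**Conclusion.** The point holds in this limited form. As written, the plan removes consented participants of randomised pharmacies from all four hospital and ED outcomes because of an event after allocation, against its own statement in section 2. It also leaves objective adherence and GP visits without a derivable window for anyone never served. For adherence alone, waiting time is absorbed into a baseline value that the model adjusts for.

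The size and direction of any bias are unknown, because the SAP reports neither non-starters nor lag by arm. The 0.9 to 3.1 points rest on assumed non-start of 5% against 10% to 15% and a rate of 40% to 50% among the never served. The 25% base rate combines admissions and ED visits, so admissions alone may be rarer, and section i.ii does not say whether it includes the unserved. If few people failed to start, or if the arms were alike, the effect is negligible. The plan should be put right because the correction is cheap and the reader cannot otherwise tell which case applies.

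**What to change.** 1. Define the linked hospital data sample as all consented participants of randomised pharmacies with linked hospital data, whether or not the interview took place.
2. For those never served, start the six-month window at the baseline survey date, for the hospital/ED, GP and adherence outcomes. Say also what date applies to anyone who consented but has no survey date.
3. Keep the service date as the main time origin for those served. Add a sensitivity analysis that starts everyone's window at the baseline survey date.
4. Report by arm the number who never started and the distribution of the survey-to-service lag.

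The cost is a change of wording and some re-cutting of linked data. Including unserved people and waiting time will dilute the estimated effect slightly. Sections i.i and i.ii show that this version was written after data had been examined, so the change should be dated and reported as such. It does not alter the separate rule in section 4.1.1 that counts a psychotropic only if it was dispensed at least twice both before and after the service. A medicine stopped for good during the wait would still drop out through that rule.

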#### 3.2 Cluster characteristics and baseline comparisons

Baseline completion data will be used to describe the characteristics of community pharmacies by the RCT groups. Between-group differences will be tested using Fisher's exact tests for categorical variables and Wilcoxon rank-sum tests for continuous variables. Details of the coding and analysis for each variable are listed below (Table 3.1).

Table 3.1 Pharmacy specific variables

Variables	Coding	Statistical analysis
Number of pharmacies	-	-
Participants recruited per	-	Wilcoxon rank-sum test
pharmacy, median(IQR)		
Location a	1=MMM1, 0=MMM2-7	Fisher's exact test
Pharmacy region b	1=ACT 2=HNE 3=NS 4=VIC	Fisher's exact test
Number of full-time pharmacists	-	Wilcoxon rank-sum test
present		

<sup>a Remoteness based on the Modified Monash Model (MMM)

#### 3.3 Consumer participants' characteristics and baseline comparisons

Baseline characteristics of participants will be presented by the RCT groups. Between-group differences will be tested using a mixed-effects linear regression if the dependant variable is continuous, mixed-effects logistic regression if the dependant variable is binary or mixed-effects ordered logistic regression if the dependant variable is ordinal. In each regression model, the RCT group will be entered as a fixed effect, and the pharmacy will be entered as a random intercept. Baseline variables common to the intervention and comparator group, coding and proposed analyses

**Table 3.2 Consumer participant-specific variables** 

are listed below (Table 3.2).

Demographic characte	ristics	
Variables	Coding	Statistical analysis
Age	Number	Mixed-effects linear regression
Gender	1=Male 0=Female	Mixed-effects logistic regression
Country of birth	1=Australian 0=Other	Mixed-effects logistic regression
Indigenous identity	1=Aboriginal or Torres Strait Islander, 0=Not Aboriginal or Torres Strait Islander	Mixed-effects logistic regression
Language primarily spoken at home	1=English, 0=Other	Mixed-effects logistic regression
Employment status	1=Employed, 0=Unemployed, disability pension, or other	Mixed-effects logistic regression
Education status	1=Year 12 or under, 2=Certificate or diploma, 3=Undergraduate or graduate degree	Mixed-effects ordered logistic regression
Self-reported health ch	paracteristics	

<sup>b ACT, Australian Capital Territory; HNE, Hunter New England; NS, Northern Sydney; VIC, Regional Victoria

Variables	Coding	Statistical analysis
Multiple mental illnesses	1=More than one mental illness,	Mixed-effects logistic regression
diagnoses	0=One mental illness	
Moderate/severe depression	1=Reported, 0=Not reported	Mixed-effects logistic regression
Moderate/severe anxiety	1=Reported, 0=Not reported	Mixed-effects logistic regression
disorder		
Bipolar disorder	1=Reported, 0=Not reported	Mixed-effects logistic regression
Schizophrenia/schizoaffective	1=Reported, 0=Not reported	Mixed-effects logistic regression
disorder		
Substance use disorder	1=Reported, 0=Not reported	Mixed-effects logistic regression
Post-traumatic stress	1=Reported, 0=Not reported	Mixed-effects logistic regression
disorder, PTSD		
Personality disorder	1=Reported, 0=Not reported	Mixed-effects logistic regression
Other mental illnesses	1=Reported, 0=Not reported	Mixed-effects logistic regression
Number of physical health	continuous number	Mixed-effects linear regression
conditions		
Diabetes	1=Reported, 0=Not reported	Mixed-effects logistic regression
Asthma	1=Reported, 0=Not reported	Mixed-effects logistic regression
Hypertension	1=Reported, 0=Not reported	Mixed-effects logistic regression
Hypercholesterolaemia	1=Reported, 0=Not reported	Mixed-effects logistic regression
Arthritis	1=Reported, 0=Not reported	Mixed-effects logistic regression
Cardiovascular disease	1=Reported, 0=Not reported	Mixed-effects logistic regression
Gastro-oesophageal reflux	1=Reported, 0=Not reported	Mixed-effects logistic regression
disease, GORD		
Cancer	1=Reported, 0=Not reported	Mixed-effects logistic regression
Chronic obstructive	1=Reported, 0=Not reported	Mixed-effects logistic regression
pulmonary disease, COPD		
Osteoporosis	1=Reported, 0=Not reported	Mixed-effects logistic regression
Other health conditions	1=Reported, 0=Not reported	Mixed-effects logistic regression
General health	1=Excellent, 2=Very good, 3=Good,	Mixed-effects linear regression
	4=Fair, 5=Poor	
Self-reported hospital	1=Yes, 0=No	Mixed-effects logistic regression
admissions during previous 6		
months		
Mental healthcare plan	1=Yes, 0=No/not sure	Mixed-effects logistic regression

#### 4. Proposed outcome analysis

#### 4.1 Primary outcome

Difference in psychotropic medication adherence rates between the IG and CG at 6-month follow-up, as objectively assessed through PBS data and pharmacy dispensing data. Self-reported assessment of adherence to all prescribed medications, as subjectively assessed using the Reported Adherence to Medication (RAM) Scale. These will be considered co-primary outcomes measuring medication adherence using different data samples. Details of the data used, definition of the variables and proposed analyses are outlined below.

**Primary analysis:** A mixed-effects logistic regression model will be applied to compare the medication's adherence rate over the 6 months after initial intervention/comparator service between IG and CG. RCT group will be entered as fixed effect and pharmacy entered as a random intercept to account for possible non-independence of observations from participants who attend the same pharmacy. The baseline value of the outcome variable will be included as a covariable in the model. The effect estimate will be reported as an odds ratio with 95% confidence interval.

**Sensitivity analysis:** To assess the robustness of the results, sensitivity analysis will be performed for this primary outcome, using the linked PBS data sample.

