## 4.1.2 Subjective assessment of medication adherence

**Data and participants:** The full analysis sample for this primary outcome will be the survey completion data sample.

**Definition:** Subjective medication adherence is measured using the Reported Adherence to Medication Scale (RAM).

**Primary analysis:** The difference in the RAM scores between IG and CG at 6-month follow-up will be compared using a mixed-effects linear model with baseline RAM scores adjusted. The RCT group will be entered as a fixed effect and the pharmacy will be entered as a random intercept to account for possible non-independence of observations from participants who attend the same pharmacy. The effect estimate will be reported as the mean difference in RAM scores and 95% confidence interval.

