#### 4.2 Secondary outcomes

Secondary outcomes will be the differences in the following variables between IG and CG at the 6-month follow-up point or during the six months after the initial intervention/comparator service. Different samples will be used to analyse the secondary outcomes based on the data required for each specific analysis.

Overall, for binary and ordinal outcomes, mixed-effects logistic/ordered logistic regression models will be applied to compare these outcomes between the intervention and comparator groups. For continuous outcomes, mixed-effects linear regression models will be applied; and for count data, mixed-effects Poisson regression models will be used. In all mixed-effects models, the treatment arm will be entered as a fixed effect and the pharmacy will be entered as a random intercept to account for possible non-independence of observations from participants who attend the same pharmacy. Baseline values of the outcome variable will be included as a covariate in these models when possible. Between-group comparisons will be reported as mean difference, odds ratio or incidence rate ratio with 95% confidence intervals.

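### Pharmacies are randomised within four regions, but the specified models omit region; the test stays valid but loses power if outcomes differ by region

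*SAP*

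**What the plan says.** On the design, SAP section 1 states: "Community pharmacies will be randomised using a 1:1 ratio, to either the Intervention Group (IG) or Comparator Group (CG) within four Australian regions". The word stratified is not used for the randomisation, but the natural reading is that region is a randomisation stratum.

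On the analysis, the general rule in section 2 is: "Comparative analyses will allow for the clustered nature of the data and baseline values will be adjusted in the models". The specific models follow it:

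- Section 4.1.1 (objective adherence, mixed logistic): "RCT group will be entered as fixed effect and pharmacy entered as a random intercept", and "The baseline value of the outcome variable will be included as a covariable in the model".
- Section 4.1.2 (RAM score): groups are "compared using a mixed-effects linear model with baseline RAM scores adjusted", again with group as a fixed effect and a pharmacy random intercept.
- Section 4.2 (secondary outcomes): "In all mixed-effects models, the treatment arm will be entered as a fixed effect and the pharmacy will be entered as a random intercept", with the baseline value added where possible.

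Region is recorded for every pharmacy and coded "1=ACT 2=HNE 3=NS 4=VIC" in Table 3.1, but it is used only to describe and compare pharmacies at baseline. Location enters the outcome analyses once, in section 2: "Stratified analyses will be conducted based on the metropolitan or non-metropolitan location of community pharmacies". Table 3.1 lists that location variable separately from region. The SAP gives no reason for leaving region out of the models.

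**The concern.** Randomising within region balances the arms on region, so regional differences in outcome cannot contribute to the error in the treatment contrast. A model without region does not know this. It counts regional differences as pharmacy-to-pharmacy variation and charges them to the standard error of the treatment effect. The reported precision is then worse than the design actually achieved.

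The pharmacies limit the information in a cluster trial, so inflation of the between-pharmacy variance goes straight into the confidence interval. It affects both co-primary outcomes. The planned metropolitan/non-metropolitan analyses do not repair this: they use a different variable and put no region term in the main models.

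**Working it through.** **Inputs from the SAP.** Clusters are pharmacies, allocated 1:1 within four regions (section 1). Model terms are arm, pharmacy random intercept and baseline value (sections 2, 4.1.1, 4.1.2, 4.2). The significance level is 5% (section 2), taken here as two-sided because 95% intervals are reported. The SAP gives no number of pharmacies, cluster size, ICC, regional difference or power, so there is no figure to reproduce. Everything below rests on assumed values.

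**Closed form.** With total outcome variance 1, m participants per pharmacy and intracluster correlation ICC, the variance of a pharmacy mean is ICC + (1 − ICC)/m. If region explains a share r of the between-pharmacy variance, the variance relevant to the treatment contrast is ICC + (1 − ICC)/m − r × ICC. The model without region overstates the standard error by the square root of the ratio of the two. The actual type I error is 2 × [1 − Φ(1.96 × ratio)]. If 80% power was planned on the region-adjusted variance, the power without region is Φ(2.80 − 1.96 × ratio), where 2.80 = 1.96 + 0.84.

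With m = 10 assumed:

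| ICC | r | variance ratio | SE ratio | type I error | power |
|---|---|---|---|---|---|
| any | 0 | 1 | 1.000 | 5.0% | 80% |
| 0.05 | 0.3 | 0.145/0.130 | 1.056 | 3.8% | 77% |
| 0.05 | 0.5 | 0.145/0.120 | 1.099 | 3.1% | 74% |
| 0.10 | 0.3 | 0.190/0.160 | 1.090 | 3.3% | 75% |
| 0.10 | 0.5 | 0.190/0.140 | 1.165 | 2.2% | 70% |

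The power column depends on its premise. If 80% was instead planned on the total ICC, the model without region has power Φ(0.84 × ratio), which is 81% to 84% over the same range. The model with region has Φ(2.80 × ratio − 1.96), which is 84% to 90%.

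**Simulation, linear model.** Assumed: 48 pharmacies of 6, four equal regions, ICC 0.05 within region, within-region SD 1, true effect 0.4 SD for power, 20,000 runs. The true standard error should be √[2 × (0.05 + 0.95/6)/24] = 0.132.

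| region variance | SE without region | type I error without | power without | power with |
|---|---|---|---|---|
| 0 | 0.131 | 4.8% | 84.5% | 84.4% |
| 0.02 | 0.137 | 4.2% | 82.0% | 84.2% |
| 0.05 | 0.147 | 2.7% | 78.1% | 84.5% |
| 0.10 | 0.161 | 1.6% | 71.2% | 84.1% |

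With region in the model, the standard error stays at 0.131 and type I error at 4.7% to 5.2%. The estimate is unbiased either way. The pattern is the same with 24 and 64 pharmacies.

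**Simulation, logistic model.** Assumed: 48 pharmacies of 6, pharmacy SD 0.4 on the logit scale, odds ratio 2 for power, 500 runs. With the extreme regions at ±0, ±0.4 and ±0.8 logits, type I error without region is 5.6%, 4.0% and 2.4%. Power is 77%, 69% and 55% without region, against 79%, 74% and 72% with it. The mean log odds ratio barely moves (0.679 without and 0.686 with region at the largest regional effect).

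Neither the closed form nor the simulations include the baseline outcome covariate. It would absorb part of any stable regional difference and so shrink these gaps.

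**The case against.** The strongest reply is that nothing here is invalid. The pharmacy random intercept absorbs regional variation, the linear estimate is unbiased, and the error is in the conservative direction. That stands. A reader might infer from the mismatch between design and model that the standard errors are simply wrong or that false positives are more likely; the calculations show neither.

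The size also rests wholly on assumptions. The SAP does not show that regions differ, and the baseline value already in the models will take up some of any difference. That stands too. A reader might read the table as showing that the trial drops below 80% power. The SAP does not support this, because it does not say on what variance the trial was sized.

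A further reply concerns the metropolitan/non-metropolitan analyses. One might infer that two separate results will be set against each other to claim effect modification. Section 2 says only that stratified analyses will be done, not how they will be interpreted. Nor can one tell from the SAP whether location also played a part in allocation; it names region only and refers design details to the published protocol.

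Finally, adding terms has risks. Section i.ii reports that negative binomial models for hospital use failed to converge and that almost three quarters of participants had no such record, so three more parameters could make matters worse. Sections i.i and i.ii show that data had been examined by this version, so a change to the primary model needs a reason. In the logistic simulation with the largest regional effect, the region-adjusted model rejected 7.2% of the time under the null. With 500 runs the simulation error is √(0.05 × 0.95/500) = 1.0 percentage point, so part of the excess may be chance and part a small-sample effect of normal critical values. These points narrow the fix; they do not remove the case for it in the co-primary models.

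**Conclusion.** The point holds as one of efficiency and of consistency between design and analysis, not of validity. The SAP allocates within four regions, names region as a recorded variable, and leaves it out of both co-primary models and the general secondary model without explanation.

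The consequence is conditional. If outcomes do not differ by region after baseline adjustment, nothing is lost. If they do, standard errors are too large, by about 6% to 16% under the closed-form assumptions (10 per pharmacy, ICC 0.05 to 0.10, region explaining 30% to 50% of between-pharmacy variance, no absorption by the baseline covariate). The simulated linear range was 0% to about 22% (0.161/0.132) under its own assumptions. None of these figures can be derived from the SAP.

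The change is worth making because the possible loss falls on both co-primary outcomes and can be avoided with data already held. In the simulations, including region cost almost no power when regions did not differ.

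**What to change.** - In sections 4.1.1 and 4.1.2, add region as a fixed effect (three indicators) alongside arm, baseline value and pharmacy random intercept, and amend the general rule in section 2 to match.
- In section 4.2, add region to the secondary models where it can be estimated. For sparse hospital and emergency outcomes, state in advance that the model without region is used if the model with it does not converge.
- Log this as a dated amendment. The reason to record is that region is fixed by the randomisation and is not chosen from the data. If the sponsor prefers to leave region out, say why.
- State that any claim of a different effect in metropolitan and non-metropolitan pharmacies will rest on an arm-by-location interaction, labelled exploratory.

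The cost is a few lines of SAP text and three parameters per model. No new data are needed.
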